3.1.6 Disease Relapse/Flare

Relapse is defined as the recurrence or new onset of disease attributable to active GPA/MPA.

By Pediatric Vasculitis Activity Score (PVAS), major relapse/flare is defined as the recurrence or new onset of potentially organ- or life-threatening disease (i.e., the

recurrence or new appearance of one or more major PVAS items listed in [Table 2](#) or disease that is severe enough to require treatment with CYC).

By PVAS, minor relapse/flare is defined as the recurrence or new onset of disease that is neither potentially organ- or life-threatening (i.e., the recurrence or new appearance of at least three minor PVAS items listed in [Table 2](#)).

By BVAS/WG, major relapse/flare is defined as the recurrence or new onset of potentially organ- or life-threatening disease (i.e., the recurrence or new appearance of one or more major BVAS/WG items listed in [Table 3](#) or disease that is severe enough to require treatment with CYC).

By BVAS/WG, minor relapse/flare is defined as the recurrence or new onset of disease that is neither potentially organ- or life-threatening (i.e., the recurrence or new appearance of at least three minor BVAS/WG items listed in [Table 3](#)).

Table 2 PVAS Features of Limited and Severe AAV

Severe (Major) PVAS Items ^a	Limited (Minor) PVAS Items ^b
	Myalgia
Gangrene (extensive necrosis)	
Significant proptosis	Arthralgia or arthritis
Red eye scleritis ^c	Fever $\geq 38^{\circ}\text{C}$
Sudden visual loss	Weight loss of $\geq 5\%$ body weight
Retinal vasculitis/retinal vessel thrombosis/retinal exudates/hemorrhages	Polymorphous exanthema
Subglottic stenosis/hoarseness /stridor	Livedo
Sensorineural hearing loss	Panniculitis
Massive hemoptysis/alveolar hemorrhage	Purpura
Respiratory failure	Skin nodules
Loss of pulses	Infarct (nail edge lesion, splinter hemorrhage)
Ischemic cardiac pain	Ulcer (full-thickness necrosis)
Cardiomyopathy	Other skin vasculitis
Congestive cardiac failure	Mouth ulcers/granulomata
Peritonitis	Genital ulcers
Bowel ischemia	Adnexal inflammation
Hematuria with red cell casts ^d	Red eye episcleritis ^c
Rise in creatinine $>10\%$ or creatinine clearance or GFR fall $>25\%$	Red eye conjunctivitis/blepharitis/keratitis
Meningitis/encephalitis	Uveitis
Organic confusion/cognitive dysfunction	Blurred vision
Seizures (not hypertensive)	Nasal discharge/crusts/ulcers/granuloma

Severe (Major) PVAS Items ^a	Limited (Minor) PVAS Items ^b
Stroke	Paranasal sinus involvement

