4.1.1 Inclusion Criteria

Patients must meet the following criteria for study entry:

- Written informed consent for study participation obtained from patient's parents or legal guardian, with assent as appropriate by the patient, depending on the patient's level of understanding
- Age at screening between ≥ 2 and < 18 years
- Diagnosis of GPA (EULAR/PRINTO/PRES 2008, Ankara criteria for childhood WG [Özen et al. 2010]; see [Appendix 5](#)) or diagnosis of MPA (according to the Chapel Hill Consensus Conference [Jennette 1994]; see [Appendix 6](#))
- Newly diagnosed patients or patients with relapsing disease according to the following definition:
 - The recurrence or new onset of potentially organ- or life-threatening disease (i.e., one or more major BVAS/WG items listed in [Table 3](#) or disease severe enough to require treatment with CYC).
- For patients of reproductive potential (males and females), use of a reliable means of contraception (e.g., abstinence, hormonal contraceptive patch, intrauterine device, physical barrier) throughout their study participation

- For all eligible patients, mandatory prophylactic treatment for *Pneumocystis jiroveci* infection

Table 3 BVAS/WG Features of Limited and Severe AAV

Severe (Major) BVAS/WG Items ^a	Limited (Minor) BVAS/WG Items ^b
Cutaneous gangrene	Arthralgias/arthritis
Scleritis	Fever (> 38°C)
Retinal exudates/hemorrhage	Purpura
Sensorineural hearing loss	Skin ulcer
Mesenteric ischemia	Mouth ulcers
Alveolar hemorrhage	Conjunctivitis/episcleritis
Red blood cell urinary casts	Orbital mass/proptosis
Rise in serum creatinine 30% over baseline value	Uveitis
Aseptic meningitis	Bloody nasal discharge/nasal crusting
Spinal cord lesions	Sinus involvement
Cerebrovascular accident caused by vasculitis	Swollen salivary gland
Cranial nerve palsy	Subglottic inflammation
Sensory peripheral neuropathy	Conductive deafness ^c
Motor mononeuritis multiplex	Pericarditis
	Pleurisy
	Pulmonary nodules or cavities
	Other pulmonary infiltrates secondary to vasculitis
	Endobronchial lesions
	Hematuria

AAV=ANCA-associated vasculitis; ANCA=anti-neutrophil cytoplasmic antibody
 BVAS=Birmingham Vasculitis Activity Score; WG=Wegner's granulomatosis.

^a Any of these items must be attributable to the active underlying disease.

^b Minor items with a significant risk of morbidity may be classified as severe (i.e., BVAS/WG 3).

^c Additional testing may be required to make the diagnosis.

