- Treatment with rituximab or other biologic B cell-targeted therapy (e.g., anti-CD19, anti-CD20, anti-CD22, or anti-B-lymphocyte stimulator [BLys]/BAFF) within 6 months prior to baseline visit
- Previous treatment with an anti-alpha 4 integrin antibody or co-stimulation modulator
- Previous treatment with other cell-depleting therapies, including, but not limited to, investigational agents (e.g., alemtuzumab [CAMPATH[®]], anti-CD4, anti-CD5, anti-CD3, and anti-CD11a)
- Receipt of oral or IV CYC within the previous 4 months prior to the baseline visit
- Receipt of infliximab within the previous 3 months prior to the baseline visit

- Receipt of adalimumab within the previous 2 months prior to the baseline visit
- Receipt of etanercept within the previous 1 month prior to the baseline visit
- Treatment with any investigational agent within 28 days of baseline or 5 half-lives of the investigational drug (whichever is longer)
- Receipt of any live or attenuated vaccine within 28 days prior to baseline
 - It is recommended that a patient's vaccination record and the need for immunization should be carefully reviewed and updated prior to receiving rituximab (see Section 4.4.3).
- Intolerance or contraindications to IV glucocorticoids

In case of receipt of any other immunosuppressant therapy (apart from corticosteroids), contact the Sponsor.

Exclusions Related to Laboratory Findings

- Positive serum human chorionic gonadotropin measured at screening or a positive pregnancy test prior to the first rituximab infusion for participants of childbearing potential
- Positive tests for hepatitis B surface antigen (HBsAg), hepatitis B core antibody (HBcAb), hepatitis B virus (HBV), or hepatitis C serology
- Level of IgM below LLN of age-specific reference range
- *Level of IgG below 5.65 mg/ml*
- Absolute neutrophil count (ANC) $< 1.5 \times 10^3/\mu\text{L}$
- Platelet count $< 130 \times 10^3/\mu\text{L}$
- Estimated GFR $< 15 \text{ mL/min/1.73 m}^2$ (calculated using the Schwartz formula; see Appendix 3)
- Alanine aminotransferase (ALT) or aspartate aminotransferase (AST) levels $> 2.5 \times$ the upper limit of normal (ULN) (for age and sex) that cannot be attributed to underlying GPA or MPA

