Native Hawaiian or other Pacific Islander	nn (xx.x%)
White	nn (xx.x%)
Multiple	nn (xx.x%)
Other	nn (xx.x%)
Unknown	nn (xx.x%)
Height (cm) ASL.BWT	
n	nnn
Mean (SD)	xx.x (xx.x)
Median	xx.x
Q1 – Q3 (IQR)	xx.x – xx.x (xx.x)
Min–Max	xx–xx

	Rituximab (N=nnn)
Weight (kg) ASL.BWT	
n	nn
Mean (SD)	xx.x (xx.x)
Median	xx.x
Q1 – Q3 (IQR)	xx.x – xx.x (xx.x)
Min–Max	xx–xx
Body-mass index (kg/m2) ASL.BBMI	
n	nn
Mean (SD)	xx.x (xx.x)
Median	xx.x
Q1 – Q3 (IQR)	xx.x – xx.x (xx.x)
Min–Max	xx–xx
Concomitant Diseases (continuing at Baseline)	
n	nn
No concomitant diseases	nn (xx.x%)
1 concomitant disease	nn (xx.x%)
2 concomitant diseases	nn (xx.x%)
>=3 concomitant diseases	nn (xx.x%)
Smoking history	
n	nn
Current	nn (xx.x%)
Previous	nn (xx.x%)
Never	nn (xx.x%)
Alcohol history	
n	nn
Current	nn (xx.x%)
Previous	nn (xx.x%)
Never	nn (xx.x%)

Estimated GFR (Schwartz formula) (mL/min/1.73 m2)	
n	nn
Mean (SD)	xx.x (xx.x)
Median	xx.x
Q1 – Q3 (IQR)	xx.x – xx.x (xx.x)
Min–Max	xx.x–xx.x
immunofluorescence (IF) ANCA status	
Negative	nn (xx.x%)
cANCA	nn (xx.x%)
pANCA	nn (xx.x%)
MPO	nn (xx.x%)
PR3	nn (xx.x%)
BVAS/WG Score	
n	nn
Mean (SD)	xx.x (xx.x)
Median	xx.x
Q1 – Q3 (IQR)	xx.x – xx.x (xx.x)
Min–Max	xx.x–xx.x

Current Disease Status

n	
Severe Flare/New Disease	nn (xx.x%)
Limited Flare/New Disease	nn (xx.x%)
Persistent Severe Disease	nn (xx.x%)
Persistent Limited Disease	nn (xx.x%)
Remission	nn (xx.x%)

BVAS/WG PGA

n	nn
Mean (SD)	xx.x (xx.x)
Median	xx.x
Q1 – Q3 (IQR)	xx.x – xx.x (xx.x)
Min–Max	xx.x–xx.x

PVAS Score

n	nn
Mean (SD)	xx.x (xx.x)
Median	xx.x
Q1 – Q3 (IQR)	xx.x – xx.x (xx.x)
Min–Max	xx.x–xx.x

PVDI Score

n	nn
Mean (SD)	xx.x (xx.x)
Median	xx.x
Q1 – Q3 (IQR)	xx.x – xx.x (xx.x)
Min–Max	xx.x–xx.x

[figure not shown]
PVDI Average School Absence (days)

[figure not shown]
n	nn
=<1	nn (xx.x%)
>1 - 4	nn (xx.x%)
>4 - 10	nn (xx.x%)
>10	nn (xx.x%)

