7. SAFETY LABORATORY ANALYSES

7.1 Safety Laboratory Analyses

Safety hematology and serum chemistry laboratory samples are taken during each planned study visit.

Treatment-emergent clinically relevant laboratory test abnormalities are to be reported as adverse events on the Adverse Event eCRF and so will be reported as AEs. This is required for planned samples taken at study visits and also for any unscheduled samples taken.

For hematology and chemistry parameters, following summaries will be produced:

- Descriptive summaries, including changes from baseline, of values at baseline and throughout the study.
- The number of patients with values outside the normal upper and lower limit at each visit.

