7.4 Laboratory Output Specifications

ID: LB001SP
 
Laboratory Test results and Change from Baseline by Visit
	
STREAM Template: LBT01
 
Analysis Population: Safety Evaluable Population
 
Analysis Variables: Single output file with separate page for each lab parameter as required by the protocol. Create tables for:
 
 Hematology: hematocrit, hemoglobin, red blood cells and indices (mean corpuscular volume, mean cell hemoglobin, mean corpuscular hemoglobin concentration), white blood cells, absolute differential [neutrophils, lymphocytes, monocytes, basophils], and platelet counts Serum chemistry: ALT/SGPT, alkaline phosphatase, AST/SGOT, calcium, chloride, creatinine, glycosylated hemoglobin (HbA_{1c}), phosphate, potassium, sodium, total bilirubin (direct and indirect will be performed if total bilirubin is greater than the ULN), total protein, urea, uric acid 
Sort order for tables: alphabetical by lab test (within hematology and chemistry)
 
Statistics and Calculation Methods: Per standard display.
 
Analysis visits to include are: Baseline, Weeks 1 to 3, Months 1, 2, 4, 6, 12 and 18. Values at visits to include only patients for whom a baseline value is included.
 
Numeric Precision and Formatting of Statistics: See mockup

---	---

Laboratory Test: SGPT/ALT (U/L)

Rituximab
(N=25)

Visit	Value at Visit	Change from Baseline
Baseline		
n	24	
Mean (SD)	25.54 (22.20)	
Median	17.00	
Q1 - Q3 (IQR)	xx.x - xx.x (xx.x)	
Min - Max	7.0 - 79.0	
Week 1		
n	21	20
Mean (SD)	27.43 (21.50)	1.75 (12.47)
Median	17.00	4.00
Q1 - Q3 (IQR)	xx.x - xx.x (xx.x)	xx.x - xx.x (xx.x)
Min - Max	7.0 - 95.0	-34.0 - 19.0
...		

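### No readable SAP output summarises eGFR after baseline, so change from baseline in raw creatinine mixes renal change with growth, by up to about 11% at Month 18 under the growth assumed here

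*SAP*

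**What the plan says.** - **Population.** Protocol 4.1.1 admits children and adolescents: "Age at screening between ≥ 2 and < 18 years".
- **eGFR before treatment.** Protocol 4.1.2 excludes patients with an estimated GFR below 15 mL/min/1.73 m², "calculated using the Schwartz formula; see Appendix 3". The SAP baseline table (4.3, output DM001SP) has a row for "Estimated GFR (Schwartz formula) (mL/min/1.73 m2").
- **Creatinine after baseline.** LB001SP in SAP 7.4 gives value at visit and change from baseline for a list that begins "Serum chemistry: ALT/SGPT, alkaline phosphatase, AST/SGOT, calcium, chloride, creatinine, glycosylated hemoglobin" and also includes urea. It does not include eGFR. On timing it states: "Analysis visits to include are: Baseline, Weeks 1 to 3, Months 1, 2, 4, 6, 12 and 18". All ages are pooled, and SAP 3.4 rules out subgroup analyses.
- **Data collected.** SAP 7.1 states: "Safety hematology and serum chemistry laboratory samples are taken during each planned study visit". The schedule of assessments (Protocol Appendix 1, SAP Appendix 2) has height at screening, at baseline and from Month 1 onward, but not at Weeks 1 to 3. SAP 8 already summarises height by visit.
- **Other readable renal information.** LB004SP classifies the same chemistry analytes as low, normal or high by visit and baseline status. A listing of normal ranges is grouped by age and sex. LB006SP and LB007SP are CTCAE shift tables for chemistry and urinalysis.

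**The concern.** The plan uses a height-adjusted renal measure to admit and describe patients, then follows them with an unadjusted one. The baseline eGFR has no follow-up value to be compared with. In growing children, a rise in creatinine can come from lost kidney function, from growth, or from both. A flat creatinine can conceal recovery.

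This matters because Protocol 1.1 names progressive renal failure as one of the two main sources of morbidity and mortality in childhood disease, and cites long-term renal impairment in 17% to 40% of patients across studies. The study has a single arm, so no control group shares the growth drift and lets it cancel.

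**Working it through.** The documents give no figure to reproduce here, so the task is to size the drift.

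**Assumptions.** Protocol Appendix 3, which holds the Schwartz formula, is redacted. I take its form as eGFR = k × height / creatinine, with k fixed within a patient. Starting height (h₀) and growth rate (v) are not in the documents. I use 110 to 165 cm and 2 to 8 cm/year as the main range, with wider extremes below.

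**Formula.** With eGFR and k constant, creatinine(t) / creatinine(0) = height(t) / height(0) = (h₀ + v·t) / h₀. The growth-only rise is therefore v·t / h₀, where t = (study day − 1) / 365.25 years.

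| Visit (study day) | t, years | 2 cm/year from 165 cm | 6 cm/year from 130 cm | 8 cm/year from 110 cm |
|---|---|---|---|---|
| Month 1 (29) | 0.077 | 0.1% | 0.4% | 0.6% |
| Month 2 (60) | 0.162 | 0.2% | 0.7% | 1.2% |
| Month 4 (120) | 0.326 | 0.4% | 1.5% | 2.4% |
| Month 6 (180) | 0.490 | 0.6% | 2.3% | 3.6% |
| Month 12 (365) | 0.997 | 1.2% | 4.6% | 7.2% |
| Month 18 (545) | 1.489 | 1.8% | 6.9% | 10.8% |

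For example, the upper Month 18 value is 8 × 1.489 / 110 = 10.8%. At the extremes, Month 18 drift is 0% with no growth and 10 × 1.489 / 90 = 16.5% for 10 cm/year from 90 cm.

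**Effect on interpretation.** For fractional height growth g and creatinine change c, the eGFR ratio is (1 + g) / (1 + c).

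- Creatinine up 10%, no growth: 1 / 1.10 = 0.909, an eGFR fall of 9.1%.
- Creatinine up 10%, height up 7%: 1.07 / 1.10 = 0.973, an eGFR fall of only 2.7%.
- Creatinine flat, height up 7%: an eGFR gain of 7%.
- eGFR down 25%, no growth: creatinine up 1 / 0.75 − 1 = 33.3%.
- eGFR down 25%, height up 7%: creatinine up 1.07 / 0.75 − 1 = 42.7%.

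Growth biases the reading in one direction. It is a few percent at most in the induction phase. By Months 12 to 18 it is comparable with a modest renal change, and it stays well below the creatinine rise that goes with a 25% fall in GFR.

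**The case against.** **Creatinine is not the only renal summary.** A reader might infer that it is, but the SAP does not support that. Urea is in LB001SP, LB004SP compares values with ranges listed by age and sex, the CTCAE tables cover chemistry and urinalysis, and clinically relevant abnormalities become adverse events. This softens the point. None of these outputs gives a growth-adjusted change in renal function, however. A child whose creatinine is high at baseline stays in the sustained-high row through further decline or partial recovery that remains above the limit.

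**The primary outcome is not change in creatinine.** Protocol 3.4.1.1 and SAP 2.1.1 make it the frequency of laboratory abnormalities. LB004SP and the shift tables are closest to that, and LB001SP is supporting description. This stands, and it limits the importance of the point. No test or readable decision rule depends on the mean creatinine change.

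**Growth alone does not score a relapse.** The PVAS list in Protocol Table 2 includes a creatinine rise above 10%, which the Month 18 drift can approach or pass. A reader might infer false relapses. Footnote a to that table requires items to be attributable to active disease, so the 10% serves only as a yardstick of size. The corresponding BVAS/WG item in Table 3 is a 30% rise, far above the drift.

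**Redaction.** The efficacy and pharmacodynamic specifications are blacked out, and GFR is in the schedule's abbreviation list without a readable row. A by-visit GFR output may exist there, so absence can be claimed only for the readable text.

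**Conclusion.** The point holds in a limited form. The readable plan drops eGFR after baseline although its inputs are collected from Month 1, and the creatinine change in LB001SP then carries an upward growth component. Its size is 0.6 to 3.6% at Month 6 and 1.8 to 10.8% at Month 18 for growth of 2 to 8 cm/year from 110 to 165 cm, and zero in fully grown adolescents. These figures rest on the assumed growth, on the assumed form of the Schwartz formula and on a constant k.

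It would go too far to say that renal change cannot be told from growth. The drift is small during induction, and large losses of function remain visible throughout. Nor should the drift be projected over several years of follow-up as a fault of this table, because LB001SP stops at Month 18. What is lost is a fair reading of modest decline or recovery at Months 12 to 18. That is worth correcting because the correction is nearly free.

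**What to change.** Unless a redacted output already does this, the sponsor should amend LB001SP as follows:

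1. Add Schwartz eGFR, by the Appendix 3 formula used for eligibility and with that visit's own height and creatinine, as value and change from baseline at Months 1, 2, 4, 6, 12 and 18. Leave out Weeks 1 to 3, where height is not scheduled.
2. Add a descriptive count of patients whose eGFR has fallen more than 25% from baseline. The figure is the GFR limit already printed in Protocol Table 2. The count would be a summary of size and would not classify relapse.
3. Keep raw creatinine as supportive.
4. If the Schwartz constant differs by age or sex, state which constant applies when a child crosses a boundary, for example by holding the baseline constant for the change analysis. Otherwise eGFR would show an artificial step.

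The cost is one derived variable, one more table page and the rule in item 4. No new data are needed. If a by-visit eGFR output exists in the redacted sections, a cross-reference from SAP 7.4 is enough.

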3.1.3 Follow-Up Phase

Following the remission induction phase, patients will be followed for a minimum of 12 months with visits every 3 months, in accordance with the schedule of assessments (see [Appendix 1](#)). The optimal treatment after rituximab induction for GPA or MPA has

not been established in adults or in pediatric patients. After Month 6, patients who are protocol remission failures or experience disease flare that cannot be controlled by glucocorticoids alone should receive treatment in accordance with local standard of care at the discretion of the investigator and will remain in the study (see Section 4.4.2.1).

After Month 6, if patients require retreatment with rituximab, additional courses will be provided by the Sponsor until the common closeout date. Retreatment with rituximab is at the discretion of the investigator and may be considered based on disease activity, previous response to treatment, and the investigator's assessment of the risks with rituximab.

After Month 18, patients will be followed at study visits every 3 months until the common closeout date. The procedures performed at the follow-up visits will be similar to those performed at the Month 18 visit. After the common closeout date, patients whose B cells remain depleted and/or who have immunoglobulin levels below the lower limit of normal (LLN) for the population will enter extended follow up.

The schedule of assessments is provided in [Appendix 1](#).

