3.3 Visit Windows

For summarization by time-point data will be assigned to an analysis visit based on the date of the assessment relative to the date of study treatment Day 1 (treatment start). The visit assessment windows given in Table 1 will be used to assign data to planned study assessments:

Table 1 Analysis Visit Time-point Windows

Assessment Month	Planned Treatment Day ⁽¹⁾	Day Number ⁽¹⁾ Range
Baseline	1	Day 1
Week 1	8	Days 5 – 11
Week 2	15	Days 12 – 18
Week 3	22	Days 19 – 25
Month 1	29	Days 26 – 44
Month 2	60	Days 45 – 75
Month 4	120	Days 105 – 135
Month 6	180	Days 165 – 210
Month 9	270	Days 240 – 300
Month 12	365	Days 335 – 395
Month 15	455	Days 425 – 485
Month 18	545	Days 500 – 590
Month 21 or Follow-up month 3	**	Planned Treatment Day ± 45 days
Month 24 or Follow-up month 6	**	Planned Treatment Day ± 45 days
...

** Planned Treatment Day = Month 18 Planned Treatment Day + 92 × (number of follow-up month /3)

Assessments made outside of these assessment windows will be listed but not used in *by time-point* summaries.

⁽¹⁾ For each patient, the day of the baseline visit will be defined as treatment day 1 and subsequent time-points will be assigned a treatment day calculated as:
(date of assessment – date of baseline) + 1

For a given measurement and analysis visit the following rules will be used to decide which value to use in the analysis:

- Protocol defined visit assessments will take priority over unscheduled visit data; that is, unscheduled visit data will only be used if there is no scheduled visit results within the same time window.
- If more than one assessment falls within the same window, then use the measurement taken nearest to the planned day. In the case of a tie, use the earlier measurement.
- Assessments made outside of these analysis visit windows will be listed but not used in by time-point summaries.

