8.1 Vital Signs Output Specifications

ID: VS001SP
 
Vital Sign Results and Change from Pre-infusion by Infusion Number in Remission Induction Phase
	
STREAM Template: VST01
 
Analysis Population: Safety Evaluable Population
 
Column Variables: Value after infusion and Change from Pre-infusion.
 
Analysis Variables: Separate tables in one file for each of: pulse rate (display as “heart rate” in the output), systolic blood pressure, and diastolic blood pressure. Use pre-infusion values only.
 
Include planned infusions (in the remission induction phase).
 
Statistics and Calculation Methods: Time-points to include are: pre-infusion and 0.25, 0.5, 0.75, 1, 1.5, 2, ... 6 hours post-infusion.
 
Numeric Precision and Formatting of Statistics: See mockup

---	--

Time-point Relative to Infusion Start		Value at Time-point	Change from Pre-infusion
Infusion 1			
Pre-infusion	n	nn	
	Mean (SD)	xxx.x (xx.x)	
	Median	xxx.x	
	Q1 – Q3 (IQR)	xx.x-xx.x(xx.x)	
	Min-Max	xxx.x-xxx.x	
0.25 hours Post	n	nn	nn
	Mean (SD)	xxx.x (xx.x)	xxx.x (xx.x)
	Median	xxx.x	xxx.x
	Q1 – Q3 (IQR)	xx.x-xx.x(xx.x)	xx.x-xx.x(xx.x)
	Min-Max	xxx.x-xxx.x	xxx.x-xxx.x
Infusion 2 ...			

ID: VS002SP
 
Vital Sign Results and Change from Baseline by Visit
	
STREAM Template: VST01
 
Analysis Population: Safety Evaluable Population
 
Column Variables: Value at visit and Change from Baseline.
 
Statistics and Calculation Methods: Analysis visits to include are: Baseline, Weeks 1 to 3, Months 1, 2, 4, 6, 9, 12, 15 and 18.
 
Values at visits to include only patients for whom a baseline value is included.
 
Numeric Precision and Formatting of Statistics: See mockup

--	--

Visit		Value at Visit	Change from Baseline
Day 1 (Baseline)	n	nn	
	Mean (SD)	xxx.x (xx.x)	
	Median	xxx.x	
	Q1 – Q3 (IQR)	xx.x-xx.x(xx.x)	
	Min-Max	xxx.x-xxx.x	
Week 1	n	nn	nn
	Mean (SD)	xxx.x (xx.x)	xxx.x (xx.x)
	Median	xxx.x	xxx.x
	Q1 – Q3 (IQR)	xx.x-xx.x(xx.x)	xx.x-xx.x(xx.x)
	Min-Max	xxx.x-xxx.x	xxx.x-xxx.x
Week 2	n	nn	nn
	Mean (SD)	xxx.x (xx.x)	xxx.x (xx.x)
	Median	xxx.x	xxx.x
	Q1 – Q3 (IQR)	xx.x-xx.x(xx.x)	xx.x-xx.x(xx.x)
	Min-Max	xxx.x-xxx.x	xxx.x-xxx.x
...			

ID: VS003SP Vital Sign Results and Changes from Baseline Above and Below Specified Limits by Visit	STREAM Template: None				
	Analysis Population: Safety Evaluable Population				

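### LB004SP leaves Months 9, 15 and every visit after Month 18 out of the reference-range laboratory counts that SAP 7.1 promises for each visit

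*SAP*

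**What the plan says.** SAP 2.1.1 and Protocol 3.4.1.1 make the frequency of laboratory abnormalities a primary safety outcome.

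SAP 7.1 describes the sampling: "Safety hematology and serum chemistry laboratory samples are taken during each planned study visit". For hematology and chemistry it then promises two summaries:

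- for the measured values themselves, "Descriptive summaries, including changes from baseline, of values at baseline and throughout the study"
- for the out-of-range counts at issue here, "The number of patients with values outside the normal upper and lower limit at each visit"

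SAP 7.4 turns these into outputs. LB004SP (laboratory abnormalities by visit and baseline status) delivers the out-of-range counts. LB001SP delivers the descriptive values and changes. Both carry the same instruction: "Analysis visits to include are: Baseline, Weeks 1 to 3, Months 1, 2, 4, 6, 12 and 18". The ID LB004SP is used twice in SAP 7.4, the second time for a listing of normal ranges; here it always means the abnormality table.

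The visits missing from that list are in the study plan. Protocol Appendix 1 and SAP Appendix 2 schedule hematology and chemistry at Months 9 and 15 and at the 3-monthly visits after Month 18. Protocol 3.1.3 says: "After Month 18, patients will be followed at study visits every 3 months until the common closeout date". SAP 3.3, Table 1, gives analysis windows for all of them: Days 240 to 300 for Month 9, Days 425 to 485 for Month 15, and a window of 45 days either side of the planned day from "Month 21 or Follow-up month 3" onward.

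**The concern.** The text and the output specification give the programmer different instructions for a primary outcome, and the SAP gives no reason for the shorter list.

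LB004SP shows one block per listed visit and no row for patients who were ever out of range. A patient who is normal at all the listed visits but low or high at Month 9, Month 15 or Month 21 is counted as normal throughout. The visit blocks cannot be added up to fill the gap, because a patient out of range at both Month 6 and Month 12 appears in both. The table therefore cannot say how many patients had an out-of-range value during the study. With the planned 25 patients, each patient missed is 1/25 = 4 percentage points of an ever-abnormal proportion.

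**Working it through.** The plan states no figure on this point, so there is none to reproduce. The check compares visit lists.

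**1. Baseline to Month 18.**

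- Scheduled (SAP Appendix 2): Baseline, Weeks 1, 2, 3, Months 1, 2, 4, 6, 9, 12, 15, 18, which is 12 visits.
- In LB004SP and LB001SP: the same without Months 9 and 15, which is 10 visits.
- Omitted: 12 − 10 = 2 of 12, or 2 of the 4 visits from Month 9 to Month 18.

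**2. After Month 18.** Visits are 3-monthly to the common closeout date and none is listed. The documents do not state how long individual patients are followed, so the length m (in months) is an assumption. Withdrawal and extended follow-up visits are not counted.

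- Visits after Month 18: p = (m − 18)/3
- Scheduled after Month 6: 4 + p
- Shown after Month 6: 2 (Months 12 and 18)
- Omitted: 2 + p

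| Assumed m | p | Omitted, of visits after Month 6 | Omitted, of all visits from Baseline (12 + p) |
|---|---|---|---|
| 18 (protocol minimum) | 0 | 2 of 4 | 2 of 12 (17%) |
| 24 | 2 | 4 of 6 | 4 of 14 (29%) |
| 36 | 6 | 8 of 10 | 8 of 18 (44%) |
| 48 | 10 | 12 of 14 | 12 of 22 (55%) |
| 60 | 14 | 16 of 18 | 16 of 26 (62%) |

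**3. Which promise is broken.** The each-visit wording in SAP 7.1 belongs to the out-of-range counts, so the direct conflict is with LB004SP. For LB001SP the promise is coverage throughout the study. That does not require every visit, but a list ending at Month 18 falls short of it for anyone followed longer.

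**4. Whether another output fills the gap.**

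- LB005SP to LB007SP (hematology, chemistry, urinalysis) tabulate the worst post-baseline CTCAE grade. They are told to use all available post-baseline data, so the omitted visits do contribute. They count grades rather than values against the reference range, and not by visit. LB005SP also points to LB001SP for its analysis visits, which conflicts with its own all-data instruction.
- LB004.1SP is a listing of laboratory abnormalities. Its specification states no visit restriction, but it gives no frequencies.
- VS003SP, the vital-sign counterpart, has the row that LB004SP lacks: patients low or high at any post-baseline time point, from all post-baseline data in the analysis.

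**The case against.** The strongest reply is that this is a mismatch of wording with little effect on what is reported. The primary outcome is not defined by reference range or by visit, and the worst-grade tables cover it from all post-baseline data. Clinically relevant abnormalities are also recorded as adverse events, including those from unscheduled samples, and AE021SP tabulates adverse events to the common closeout date. With 25 planned patients, a listing is a usable record. All of this stands, and it limits the point. It does not supply the count that SAP 7.1 promises.

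Several stronger readings are tempting but not supported:

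- *Abnormalities at the omitted visits go unreported.* They feed LB005SP to LB007SP and should appear in LB004.1SP. They are missing only from the reference-range counts.
- *The short list is a slip peculiar to the laboratory tables.* The vital-sign outputs do keep Months 9 and 15 ("Analysis visits to include are: Baseline, Weeks 1 to 3, Months 1, 2, 4, 6, 9, 12, 15 and 18"). But the steroid outputs EX007.1SP to EX007.3SP also go from Month 6 to Months 12 and 18, and the vital-sign tables show no individual visits after Month 18 either. The case rests on the promise in SAP 7.1, not on a convention across outputs. SAP 3 does name Months 6, 12 and 18 as key time points, but for confidence intervals, while binary endpoints are to be shown by visit.
- *The omission hides effects of repeat courses.* Every omitted visit does fall after Month 6, when retreatment is allowed. Its timing is at the investigator's discretion, however, so visits counted from Day 1 are not aligned to courses, and Months 12 and 18 in the same period are shown.
- *Patients are known to be followed for 36 or 60 months.* EX001.1SP has duration categories beyond 60 months, but a display category does not show that anyone reaches it.

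Rewording SAP 7.1 to name the selected visits would also remove the contradiction. It would leave the reference-range frequency incomplete.

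**Conclusion.** The point holds for LB004SP. As specified, it does not deliver the each-visit counts of SAP 7.1: it drops two of the four scheduled visits from Month 9 to Month 18 and all later ones, and it has no cumulative row. A patient out of range only at an omitted visit is in no reference-range count. LB001SP shares the list and stops at Month 18, a lesser inconsistency because SAP 7.1 asks less of it.

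The omission from Baseline to Month 18 is read directly from the documents. The larger shares after Month 18 depend on the assumed follow-up lengths. A reader might infer that the primary laboratory outcome goes unanalysed after Month 18; the all-data worst-grade tables rule that out. This is a low-priority correction to the reporting of a primary safety outcome, and it does not call the study's safety data into question.

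**What to change.** 1. Add an any-post-baseline row to LB004SP, separately for low and high, counting each patient at most once per category and using all post-baseline data in the analysis, as in VS003SP. This is the more important change. It also picks up values outside the Table 1 windows, which SAP 3.3 keeps out of by-visit summaries.
2. Add Months 9, 15 and the 3-monthly visits after Month 18 to LB004SP, and to LB001SP for consistency. The windows already exist in SAP Table 1.
3. Delete LB005SP's reference to LB001SP for analysis visits and keep its all-data instruction.

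The data are already being collected, so the cost is programming time and longer tables. Numbers at late visits will be small and will depend on enrolment date, so each late row should show its n. The cumulative row should be read with the duration of observation in EX001.1SP, because patients followed longer have more chances to be out of range.
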